17 Central venous to arterial CO₂ partial pressure difference (AVCO₂) measures the circulatory clearance of
18 tissue CO₂ and has been proven to be correlated with CO in critically ill adult patients⁵. Widening of AVCO₂
19 represents an imbalance between CO₂ clearance by CO and tissue CO₂ production. With limited data available,
20 it remains unknown whether AVCO₂ is a useful adjunctive marker for assessment CO adequacy in pediatric
21 patients after cardiac surgery with CPB.

22 Additionally, increase cytokine production both pro- (interleukin (IL)-6, IL-8, and tumor necrotic factor
23 (TNF)- α) and anti-inflammatory cytokines (IL-4, IL-10) caused by CPB-induced inflammatory activation can
24 alter multiorgan function and vascular permeability. The relationship between level of these cytokines and
25 clinical outcomes also remains uncertainty in children population.

26 We aimed to evaluate the association between AVCO₂ and inflammatory markers at 4 different time points
27 post operatively with LCOS-related poor outcome and calculate predictability of these markers to facilitate
28 earlier recognition and management LCOS in children undergone cardiac surgery with CPB.

29 30 7. Objective(s) of the study

31 **Main or Primary objective:** To compare accuracy of prediction of LCOS-related poor outcome between
32 AVCO₂ and traditional bedside surrogates (lactate, ScvO₂ and AVO₂) in children with cardiac disease who
33 undergone CPB.

[figure not shown]
34 **Secondary objectives:**

1 7.1 To evaluate association between AVCO_2 in children with cardiac disease who undergone CPB and other
 2 morbidities: 28-ventilator free day, 28-ICU free day, acute kidney injury, and deaths from any cause during
 3 hospitalization.

4 7.2 To evaluate association between level of pro- and anti-inflammatory cytokine in children who underwent
 5 CPB and LCOS-related poor outcome.

6

7 **8. Conceptual framework**

8

9 **9. Literature review**

10 AVCO_2 difference

11 A retrospective study done by Rhodes LA, et al³ evaluated correlation of AVCO_2 with other cardiac output
 12 surrogates (lactate, ScvO₂ and AVO₂) and its capacity to predict poor outcomes associated with LCOS in 139
 13 infants who underwent CPB. There were only 24.5% of poor outcome in this study. The results showed moderate
 14 correlation between AVCO_2 difference with AVO₂ ($R^2 = 0.53$; $p < 0.01$), and ScvO₂ ($R^2 = -0.43$; $p < 0.01$), but not

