15	Where: Sensitivity (p)	= 0.85
16	Precision (d); not more than 10% of p	= 0.09
17	Alpha	= 0.05

18 We applied the sensitivity of lactate > 3 mmol/L for major morbidity, which defined as at least one of
19 complications (i.e., neurological, pulmonary, gastroenteric, and need for extracorporeal membranes oxygenation or
20 ventricular-assist device, or sepsis)¹⁶.

21 Estimated patient (n_0) is 61 cases. Based on 48% of incidence of LCOS-related outcome last year in our
22 study setting, the required total sample size including non-disease and disease participants will be 128 (=61/0.48).

23 Regarding with our sample size calculation for two objectives and an estimate of 20% of unusable data
24 from a sample of 128 participants has been considered. The final sample size is 154 participants for sensitivity of
25 0.85. However, we will collect blood sample for inflammatory markers in 32 patients for preliminary analysis.

26 **9.6. Variables of the study**

27 9.6.1. Dependent variable: poor outcomes indirectly represented from low cardio output syndrome

28 - LCOS-related poor outcome is modified from the study of Drennan SE, et al and Carmona, et al^{14, 15}
29 which consisting of at least two of the following criteria within 48 hour post operatively:

- 1 a. Clinical findings suggestive of LCOS: prolonged capillary refill > 3 s, systolic blood pressure < 5th
2 percentile for age and gender, persistently elevate of LA pressure above 10 mmHg for at least 6 hr
3 , low urine output (< 1mL/kg/hr) for at least 6 hour despite diuretic use
- 4 b. Laboratory findings suggestive of LCOS: persistently elevated lactate (>2 mmol/L), metabolic
5 acidosis with an increase in the base deficit (>4 mmol/L) for at least 6 hr consecutively.
- 6 c. Vasoactive-inotropic score (VIS) \square 20
- 7 d. Any unplanned surgical reinterventions, cardiac arrest, or utilization of extracorporeal membrane
8 oxygenator (ECMO) within 48 hours
- 9 e. Left ventricular fraction less than 50% by echocardiography

10 The LCOS-related outcome will include both anatomical LCOS and physiological LCOS that caused by

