11 CPB

[figure not shown]
- 12 - Vasoactive-Inotropic Score (VIS) based on Belletti A, et al¹⁷ which is summation of dopamine dose
13 (mcg/kg/min) + dobutamine dose (mcg/kg/min) + 100 x epinephrine dose (mcg/kg/min) + 10 x milrinone
14 dose (mcg/kg/min) + 100 x norepinephrine dose (mcg/kg/min) + 10000 x vasopressin dose (U/kg/min)
15 + 50 x levosimendan dose (mcg/kg/min) + 20 x methylene blue dose (mg/kg/h) + 10 x phephylephrine
16 dose (mcg/kg/min) + 10 x terlipressin dose (mcg/min) + 0.25 x angiotensin II dose (ng/kg/min)
- 17 - Acute kidney injury (AKI) based on KDIGO guideline 2012¹⁸ defined AKI as any of following: increased
18 in SCr by \square 0.3 mg/dL within 48 hours, or increased in SCr to \square 1.5 times baseline, which is known
19 or presumed to have occurred within the prior 7 days, or urine volume < 0.5 mL/kg/h for 6 hours
- 20 - 28 ventilator free day (VFDs) and 28 ICU free day (IFDs): the number of days those patients were alive
21 and free from invasive ventilator or ICU stay within 28 days by counting the day of first operative night
22 as the first day. VFDs and IFDs will be counted as zero in non-survivor patients.

23 9.6.2. Independent variables: AVCO₂, ScvO₂, lactate, inflammatory markers at 0, 6, 12, and 24 hour after
24 operation with additional inflammatory markers at pre-operative stage

25 9.6.3. Potential confounder variables: age, gender, risk stratification for cardiac surgery (RACHS score),
26 nutritional status, duration of bypass time or aortic clamp time

27 9.6.4. Methods to minimize bias during study: we will blind the result of inflammatory markers to attendant
28 physician by sending blood sample to research lab which will not be reported in HIS system. Blood
29 sample collection and processing time will be fixed to ensure laboratory quality of the specimen and
30 its interpretation.

31 32 **9.7. Study procedure(s)/stage(s)**

1. Researcher will introduce research project verbally to cardiac pediatrics patient or their legal guardians at cardiac outpatient clinic when he/ she are scheduled to have cardiopulmonary bypass surgery at Songklanagarind Hospital. Researcher will later request patient or legal guardians to sign the informed consent when he/she is admitted in hospital 24 hours in advance.

2. If patient has already been admitted in hospital for any reason and have schedule for surgery, researcher will inform patient or legal guardians 48 hours in advance.

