3. Preoperative blood sample 1.5 mL will be collected for inflammatory markers level at the same time when patient has intravenous access preparing for NPO or other preoperative blood sample.

4. Patient goes on open heart cardiac surgery and will be admitted directly to pediatric intensive care unit (PICU) for postoperative care.

5. Blood sample for blood gas 0.3 mL for each central line catheter and arterial line catheter and inflammatory markers 1.5 mL drawn from arterial line will be collected at 0, 6, 12, and 24 hours after PICU arrival. Arterial and venous blood gas are accepted if samples are collected within 5 minutes of each other. We allow time gap for collecting blood +/- 1 hr from schedule due to unpredictable ICU occupy.

6. Attending physician provides standard care for post cardiac operation. The decision of treatment by attending physician will not be involved by researchers. Inflammatory markers results will be reported after patient is discharged from hospital to minimize influence of result to physician's decision on treatment.

1 7. Cardiologist will perform echocardiography to evaluate left ventricular function and anatomical defect
 2 that could mimic signs of LCOS within 48 hours postoperatively.

3 8. Researcher prospectively collects postoperative variables including hemodynamic variables and
 4 therapeutic interventions and patient's outcome.

5 9. The primary study endpoint is poor outcome related to LCOS. The secondary endpoints are 28-day
 6 ventilator free day, ICU free day, deaths and correlation of AVCO₂ with other cardiac output surrogates
 7 (AVO₂, ScvO₂ and arterial blood lactate).

8 10. If either central line or arterial line catheter are displaced before 24-hour, remaining data will be
 9 recorded as missing data.

10 **Describe procedures/process of the study. Show how research methodology in the study is different from
 11 the routine practice?**

Processes which are routine practice	Processes which are research
1. Pre-operative lab sampling; CBC, Coagulogram, electrolyte, group match for blood component	1. Adding inflammatory markers to pre-operative lab
2. Serial ABG sampling q 2-6 hr depend on severity of patient	2. Extra 2 blood sampling for VBG (0.3 mL each)
3. Serial VBG sampling q 24 hr	3. Mandatory blood sampling q 6 hr x 5 times for inflammatory markers (1.5 mL each)

12 **9.8. Study instrument(s) and outcome measurement(s)**

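### The plan names no primary index sample, at-risk rule or Cox time zero for predicting a 0–48 h outcome, so late marker values can report LCOS already present as predicted.

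*Combined protocol and SAP*

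**What the plan says.** The primary objective (Section 7) is "To compare accuracy of prediction of LCOS-related poor outcome between" AVCO2 and lactate, ScvO2 and AVO2. The aim at the end of Section 6 is to relate markers at four times "post operatively with LCOS-related poor outcome and calculate predictability of these markers to facilitate" earlier recognition and management of LCOS.

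The predictors in Section 9.6.2 are "Independent variables: AVCO₂, ScvO₂, lactate, inflammatory markers at 0, 6, 12, and 24 hour after" operation. Section 9.7, item 5, has samples "collected at 0, 6, 12, and 24 hours after PICU arrival", with this tolerance: "We allow time gap for collecting blood +/- 1 hr from schedule due to unpredictable ICU occupy".

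The outcome in Section 9.6.1 is a composite "which consisting of at least two of the following criteria within 48 hour post operatively". Criterion a begins "Clinical findings suggestive of LCOS: prolonged capillary refill > 3 s, systolic blood pressure < 5th" percentile, and no duration is stated for those two signs or for the VIS criterion. Criterion b begins "Laboratory findings suggestive of LCOS: persistently elevated lactate (>2 mmol/L), metabolic" acidosis, with a 6-h persistence requirement.

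Section 9.11 plans sensitivity, specificity, predictive values, ROC areas and a Cox model. Its only reference to time order is a lag in the correlations among the markers themselves. Section 6 says LCOS commonly appears 6–18 h after ICU admission.

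**The concern.** Prediction requires that the marker be measured before the event. Here the outcome window opens at the end of surgery and the markers are measured inside it. A child who meets two criteria at hour 9 and has an abnormal AVCO2 at hour 12 would count as a correctly predicted case.

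On the protocol's own timing, the 12-h sample falls in the middle of the usual onset period and the 24-h sample after it. Without an index sample and an at-risk rule, the reported accuracy mixes two quantities: prediction of LCOS yet to come and detection of LCOS already present. Only the first supports earlier recognition. Leaving the sample open also allows the time point to be chosen after the results are seen. The Cox model has the related gap that no time zero is given and nothing is said about how values measured after it enter the model.

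**Working it through.** **1. The plan's own figure.** Section 9.5 uses sensitivity 0.85, d = 0.09 and alpha 0.05.
- n0 = 1.96² × 0.85 × 0.15 / 0.09² = 60.47, rounded up to 61 cases.
- 61 / 0.48 = 127.1, rounded up to 128. 128 × 1.2 = 153.6, rounded up to 154.

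The plan's figures reproduce. The calculation counts every 0–48 h case as usable and has no term for cases already present at the index sample.

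**2. Timing, side by side.**

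| Sample | Relative to the 6–18 h period in Section 6 |
|---|---|
| 0 h | Before it |
| 6 h | At its start |
| 12 h | Inside it |
| 24 h | After it |

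The 0-h sample is least exposed but not exempt, because signs with no stated duration could be met on arrival.

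**3. Effect on one marker.** Assume a share p of outcomes precedes the sample and the marker moves δ SD in the adverse direction after onset. Neither p nor δ is in the documents. With normal marker values, for a marker with no predictive value:

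AUC = p × Φ(δ/√2) + (1 − p) × 0.5, where Φ(0.5/√2) = 0.638 and Φ(1/√2) = 0.760.

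| p | δ = 0.5 | δ = 1 |
|---|---|---|
| 0.25 | 0.53 | 0.57 |
| 0.50 | 0.57 | 0.63 |

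With p = 0.05–0.10, as might apply to an early sample, the AUC is 0.51–0.53.

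**4. Effect on the comparison.** Section 9 cites a retrospective infant study with AUCs of 0.69 (AVCO2) and 0.74 (ScvO2), a difference of −0.05. Assume these are free of prevalent cases; the protocol does not say so. Then AUC′ = p × Φ(Φ⁻¹(AUC) + δ/√2) + (1 − p) × AUC, with p = 0.25–0.50.
- Both shift equally, by 0.5–1 SD: AVCO2 0.72–0.79, ScvO2 0.77–0.83, difference −0.04 to −0.05.
- Only AVCO2 shifts, by 0.5 SD: 0.718 to 0.746 against 0.74, difference −0.02 to +0.01.
- Only ScvO2 shifts, by 0.5 SD: 0.69 against 0.765 to 0.790, difference −0.08 to −0.10.

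No figure is given for lactate, which is part of criterion b, so a shift would mix timing with incorporation in the outcome. None is given for AVO2, because the protocol reports no AUC for it.

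**5. Precision under an at-risk rule at 12 h.** Half-width = 1.96 × √(0.85 × 0.15 / events).
- 61 events: 0.090, as planned.
- 61 × 0.75 ≈ 46 events: 0.10.
- 61 × 0.50 ≈ 31 events: 0.13.

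In the 32-child cytokine subset, 32 × 0.48 ≈ 15 events, of which about 8–12 would remain.

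**6. Why the dating rule matters.** Take an extreme assumed case: every outcome is completed uniformly over 6–18 h, and a null marker shifts by 0.5 SD when the abnormality starts, 6 h before completion. At 12 h, half the cases (about 31) are not yet complete, but all of them have started. Dating by completion keeps those 31 events and still gives AUC = Φ(0.5/√2) = 0.64. Dating by start removes the artefact but leaves no events.

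**The case against.** Several objections have force.

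- **The study is labelled diagnostic (Section 9.1), and concurrent accuracy is a legitimate question.** This is true, but the objective, the primary analysis and the ROC item all speak of prediction or predictability, and nothing says which sample answers which question.
- **Four time points may be meant for separate reporting, with the 0-h value as the natural predictor.** This is a fair reading, and it would limit the harm to the later samples. The plan does not state it.
- **The comparison between markers may be little affected.** This stands for equal shifts (step 4). A reader might infer that the plan biases the ranking for or against AVCO2. The documents do not support that, since they give no evidence of a one-sided shift. Two of the cited paediatric studies report moderate AVCO2–ScvO2 correlation and a third reports poor correlation.
- **A time origin is not wholly absent.** This is correct. Section 9.7 gives a sampling clock and Section 9.6.1 an outcome window. What is missing is a single origin for the analysis. The differing wording of the clocks should not be read as a major source of bias, because children go directly from surgery to the PICU.
- **Onset cannot be dated exactly.** This also stands. Section 9.7 describes arterial gases every 2–6 h and echocardiography within 48 h with no serial schedule, so those criteria date detection rather than onset. An at-risk rule reduces the problem without removing it.

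**Conclusion.** The point holds as an omission that affects the primary objective: no primary index sample, no at-risk rule and no Cox time zero. Used in all children, the 12-h and 24-h values would count LCOS already present as predicted and would inflate AUC and sensitivity for any marker that worsens after onset.

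The omission is certain; its size is not. The null-marker AUC of 0.53–0.63 rests on assumed shares of 25–50% and shifts of 0.5–1 SD. The effect on the AVCO2–ScvO2 contrast is small under equal shifts and material only under unequal ones, and it also rests on treating 0.69 and 0.74 as uncontaminated. It should be fixed before analysis. The study remains interpretable if that is done.

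**What to change.** Before analysis:

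1. Name one early sample, for example PICU arrival (0 h), as the primary index test for AVCO2 against lactate, ScvO2 and AVO2. Use PICU arrival as the single analysis clock and Cox time zero, with actual sampling times.
2. Record when the second criterion is first documented as met. State one dating rule for the 6-h persistence criteria (start or completion) and use the other as a sensitivity analysis. Acknowledge that echocardiographic and intermittently sampled laboratory criteria date detection. Start-dating also uses information from after the sample to decide who is at risk.
3. For the 6-h and later samples, base predictive claims only on children who have not yet met the outcome, counting events from the sample to 48 h, or use time-dependent covariates in the Cox model for LCOS. At 0 h, report how many children already meet the criteria.
4. Report 24-h values, and values in children already meeting the criteria, as concurrent detection.
5. Restate the precision for each sample time.

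The cost is SAP wording plus abstraction of criterion times from the charts, which is more than a single extra field. The statistical cost is fewer events at later samples: at 12 h, about 31–46 of 61 under the assumed shares, with a half-width of 0.10–0.13 instead of 0.09.

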21 **3.7 Name:** [name]

22 **Position:** Clinical instructor

23 **Affiliation:** Division of Pediatric Critical Care Medicine, Department of Pediatrics

24 **[contact] **Mobile [contact]

25 **E-mail:** [contact]

26 **Responsibility in the project:** recruit participant, review manuscript

27

28 **4. Student support**

29 **Check ✓ in () that apply**

30 () Not associated

31 (✓) Undergrad./post grad. [name].

32 **5. Keywords:** AVCO₂, inflammatory markers, post cardiac surgery, cardiopulmonary bypass

33 **6. Background and rationale**

34 Cardiopulmonary bypass (CPB) is a potent stimulus causing systemic inflammatory response in children
35 with cardiac disease who undergone open heart surgery. Mechanisms of inflammatory generator during CPB

1 include blood contact with CPB circuit, ischemia-reperfusion injury, heparin-protamine interactions, and surgical
2 trauma. These mechanisms aggravate the activation of complement cascade, release of endotoxin, and altered
3 cytokine production which led to low cardiac output syndrome (LCOS)¹

4 The LCOS refers to declining cardiac function in the face of an elevated demand of cardiac output which
5 may lead to multiorgan failure and death. Incidence of the LCOS is approximately 25% of children after cardiac
6 surgery¹ and commonly occurs 6- 18 hours following admission to intensive care unit². Currently, there is no
7 consensus for diagnostic criteria of the LCOS and accurate detection of early cardiac output (CO) insufficiency
8 is a challenging task especially in post-operative children. Measurement CO by using thermodilution method
9 via Swan-Ganz catheterization or transesophageal echocardiography are not applicable in pediatrics setting
10 meanwhile transthoracic echocardiography immediately after post-cardiac operation is limited due to surgical
11 wound and tissue swelling. In Songklanagarind Hospital, clinicians practically use parameters such as serum
12 lactate, central venous oxygen saturations (ScvO₂), and arteriovenous oxygen difference (AVO₂) as bedside
13 surrogates of CO. However, these parameters can be influenced by multiple factors unrelated to LCOS³.
14 Hyperlactatemia in cardiac surgery could be elevated due to post-operative stress response, use of beta-
15 adrenergic agonist, hyperglycemia, or reduce lactate clearance due to transaminitis while normal values of
16 ScvO₂ can be found despite microcirculatory dysfunction and localized tissue hypoxia⁴.

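### Only the cytokines are masked, so the primary markers may influence the treatment-based outcome criteria they are tested against; the direction and size of any bias are uncertain and no planned analysis would show it

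*Combined protocol and SAP*

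**What the plan says.** - **Masking.** Under methods to minimise bias, Section 9.6.4 states "we will blind the result of inflammatory markers to attendant" physicians. Section 9.7 step 6 withholds the cytokine results until after discharge, so that they do not affect treatment. No section masks AVCO2, ScvO2, AVO2 or lactate. Section 9.8 places the blood gas analyser in the PICU.
- **Use of the comparators.** Section 6 says clinicians at the site rely on serum lactate, "central venous oxygen saturations (ScvO₂), and arteriovenous oxygen difference (AVO₂) as bedside" surrogates of cardiac output. AVCO2 is not in that list, and Section 10.3 presents it as new.
- **Treatment.** Section 9.7 step 6: "The decision of treatment by attending physician will not be involved by researchers".
- **Outcome.** Section 9.6.1 requires at least two of five criteria within 48 hours. Criterion c is a VIS threshold of 20, and VIS is a weighted sum of drug doses. Criterion d is "Any unplanned surgical reinterventions, cardiac arrest, or utilization of extracorporeal membrane" oxygenation. Criterion e is left ventricular function on echocardiography; Section 9.7 step 7 says "Cardiologist will perform echocardiography to evaluate left ventricular function and anatomical defect" and does not state what the reader may see.
- **Analysis.** Section 9.11 plans one sensitivity analysis (physiological LCOS) and one subgroup analysis (univentricular versus biventricular repair). Neither rescores the outcome without the treatment-based criteria.

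**The concern.** The primary objective is a comparison of accuracy between AVCO2 and three markers that clinicians already know and use. If a low ScvO2 or a wide AVO2 leads staff to raise vasoactive support, the VIS can cross its threshold because of the marker reading itself. That marker then gains apparent accuracy that does not come from tracking cardiac output. Criteria c and d together can make a case with no other criterion met. The markers are read at 0 to 24 hours, inside the 48-hour outcome window, and no rule requires the outcome to follow the reading.

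The protocol recognises this mechanism for the cytokines, which serve a secondary objective, but has neither masking nor an analysis for the primary markers. The researcher also collects both the gas values and the outcome (9.7 step 8, 9.9), so knowledge of one can colour the scoring of the other. At stake is whether a reported difference between AVCO2 and ScvO2 or AVO2 reflects accuracy or the care that the readings prompted.

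**Working it through.** **The plan's own figures.** Section 9.5 gives "Sensitivity (p) = 0.85" and "Precision (d); not more than 10% of p = 0.09", with alpha 0.05. n0 = 1.96² × 0.85 × 0.15 / 0.09² = 60.47, rounded up to 61. "Based on 48% of incidence of LCOS-related outcome last year in our" setting gives 61 / 0.48 = 127.08, rounded up to 128; 128 × 1.2 = 153.6, rounded up to 154. All three reproduce. This point disputes none of them; the 48% incidence serves only to set the scale of the simulations.

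**Size of the possible bias.** The documents give no figure for how far markers guide treatment, so every input below except the two-of-five rule and the approximate incidence is an assumption.

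*Model 1* (400,000 simulated children per setting). Two markers, A (AVCO2) and S (ScvO2, sign reversed), have equal correlation of 0.4 or 0.5 with true low output. Criteria a to e have prevalence 50%, 50%, 35%, 10% and 15% and load 0.7 on true low output. Two are needed, giving incidence of about 47%. Criterion c also depends on w × S. The true difference in accuracy is 0.

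| Assumption | AUC(S) − AUC(A) |
|---|---|
| w = 0 | 0.00 |
| w = 0.3 | 0.028 to 0.035 |
| w = 0.5 | 0.044 to 0.051 |
| w = 0.7 | 0.057 to 0.064 |
| w = 0.3–0.7, residual marker correlation 0.5 | 0.015 to 0.034 |
| w = 0.3–0.7, AVCO2 also guides treatment at half weight | about 0.015 to 0.030 |
| w = 0.3–0.7, treatment lowers a, b, e by 0.15 SD per SD of treatment | 0.015 to 0.035 |
| the same at 0.30 SD | −0.002 to 0.002 |
| correlation 0.5, half-weight AVCO2 and 0.15 SD together | 0.003 to 0.008 |

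*Model 2* (300,000 per setting, correlation 0.5, a treatment-intensity variable driving both c and d, incidence about 50%). Here c and all of d, including cardiac arrest, are kept or dropped.

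| Assumption | AUC(AVCO2) − AUC(comparator), c and d in | c and d out |
|---|---|---|
| Neither marker guides treatment | −0.000 | −0.001 |
| Comparator guides moderately, treatment has no effect | −0.056 | +0.002 |
| Comparator guides strongly, no effect | −0.082 | +0.003 |
| Both guide equally, no effect | +0.001 | −0.000 |
| Comparator moderate, treatment effect 0.2 | −0.034 | +0.026 |
| Comparator moderate, effect 0.4 | −0.012 | +0.055 |
| Comparator moderate, effect 0.6 | +0.012 | +0.084 |
| Comparator strong, effect 0.6 | +0.015 | +0.127 |

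**Reading the tables.** A gap against AVCO2 appears when only the comparator guides treatment and treatment does little to a, b and e. It shrinks, vanishes or reverses as those conditions are relaxed. Dropping the treatment-based criteria restores a zero difference only if treatment has no effect. Otherwise it errs in favour of AVCO2: by 0.015 to 0.073 in Model 1 at effects of 0.15 to 0.30 SD (c dropped), and by about 0.03 to 0.13 in Model 2.

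**Scale against sampling error.** With 154 children and 48% incidence there are about 74 events and 80 non-events. At AUC 0.70 the Hanley–McNeil standard error is about 0.042. For two markers whose AUC estimates correlate 0.3 to 0.5, the standard error of the difference is 0.042 × √(2 × 0.7) = 0.050 to 0.042 × √(2 × 0.5) = 0.042. A bias at the upper end of the main range is therefore a little over one standard error.

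**The case against.** The strongest case against is that the documents do not establish a direction. A reader might infer that the design tilts the comparison against AVCO2, which has no path into treatment. The text does not support that:

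- Section 6 says the comparators are used as surrogates. It does not say that vasoactive drugs or ECMO are decided by them. Routine venous gases are only every 24 hours (table after 9.7), which limits how often ScvO2 and AVO2 could guide care outside the study.
- AVCO2 is not masked either. It can be calculated whenever paired gases are run, and the study's extra venous gases expose it as much as they expose ScvO2.
- Treatment prompted by a comparator may prevent criteria a, b and e, which lowers that comparator's apparent accuracy.
- The retrospective infant study in the literature review reports AUCs of 0.74 for ScvO2 and 0.69 for AVCO2. That a simulated gap can match this 0.05 follows from freely chosen weights and is not evidence.
- A reader might also infer that the echocardiographer is unmasked. The documents say nothing on this.

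All of this stands. It removes any claim about the net sign or a definite size, and any rule making a conclusion conditional on the reduced outcome. It does not remove the underlying point: unmasked markers, treatment-defined criteria and no analysis that shows how much those criteria matter.

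**Conclusion.** The point holds in limited form. As written, the plan lets the primary markers influence criterion c and the reintervention and ECMO parts of d, and so may bias the primary comparison. Through those criteria alone the bias is probably toward the comparators; its net direction and size cannot be known from the documents. Simulated gaps ran mostly from about 0 to 0.06 in AUC. The extremes were 0.08 against AVCO2 (strong guidance by the comparator, no treatment effect) and a reversal of 0.01 to 0.02 under strong treatment effect. These figures show a plausible scale and are not estimates. That clinicians act on the comparators is a reasonable inference from Section 6, not a stated fact. A cheap improvement is justified. Lactate's direct place in criterion b is a separate issue that masking would not cure.

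**What to change.** 1. **Section 9.11.** Prespecify a descriptive sensitivity analysis that repeats the comparison of AVCO2 with ScvO2, AVO2 and lactate, with the outcome rescored without criterion c and without reintervention and ECMO in criterion d (cardiac arrest stays). Report it beside the primary result. State that it does not remove treatment effects on a, b and e and can err in the opposite direction. If the two analyses disagree, temper any conclusion of superiority or inferiority. It is not a formal gate.
2. **Section 9.6.4.** State that AVCO2, ScvO2 and AVO2 are derived for analysis only after the outcome has been scored and locked, and that the echocardiographer reads left ventricular function for criterion e without being given the study venous gas values. Lactate and base deficit must remain available to the scorer, because criterion b needs them.

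Clinical access to results and clinical care stay as they are.

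**Cost.** Wording plus one rescoring of data already collected, with no extra staff or procedure. The repeat analysis has fewer events: in Model 1, dropping c lowered incidence from about 47% to 39%, which in 154 children is about 72 versus 60 events (0.47 × 154 and 0.39 × 154). Its intervals will be slightly wider.
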